6.2 Summary of Intra-patient Dose Escalation Treatment Regimen

Patients enrolled in this study will receive treatment with single-agent IMCgp100 on C1D1 and C1D8 at 20 mcg and 30 mcg per week, respectively. The majority of moderate-to-severe toxicity associated with IMCgp100 in the FIH study was observed at these 2 dose time points and included hypotension, rash, pruritus, fever, and chills (please refer to [Section 1.4](#), Clinical Experience with IMCgp100 for a full discussion of the safety data with IMCgp100). After this initial dosing period, beginning at C1D15, patients will receive an escalated dose of IMCgp100 according to the cohort into which they are enrolled (please see [Table 6-2](#) below, for dose levels to be tested). This escalated dose administered at C1D15 will be the dose used for the remainder of the treatment period unless dose reduction is implemented for toxicity. See schematic for intra-patient dose escalation regimen described in [Section 3.1](#) and [Figure 3-1](#).

In this intra-patient escalation regimen, all patients will require overnight inpatient hospitalization and a minimum of pre-dose and monitoring vital signs every 4-hours after the first administration of IMCgp100 (C1D1), after the second administration (C1D8), and after the escalated dose of IMCgp100 on C1D15 is administered. For the first 3 administrations of IMCgp100, patients should be monitored for at least 16 hours after dosing. “Inpatient hospitalization” refers to a facility with fully functional resuscitation facilities, 24 hour monitoring and physician availability.

Inpatient monitoring at Cycle 1 Day 22 (C1D22) will be determined by the toxicity observed in the C1D1–C1D15 doses as follows:

1. If the escalated dose at C1D15 administered as an inpatient does not raise safety concerns (and the patient does not experience an adverse reaction involving hypotension of grade 2 or greater), the subsequent dose at C1D22 and all subsequent doses can be administered on an outpatient basis
2. If the patient experiences hypotension requiring any medical intervention (Common Terminology Criteria for Adverse Event [CTCAE] grade 2 or greater) at C1D15, then the C1D22 dose must be administered with inpatient monitoring, similar to C1D1–C1D15. If the patient does not experience hypotension requiring medical intervention at the C1D22 dose administered as an inpatient, then all subsequent doses can be administered on an outpatient basis

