6.9.2 Cytokine Release Syndrome

Cases of CRS have been observed across the IMCgp100 clinical trials (as of 12 August 2018, CRS cases have been seen in 6% of patients in the current study overall, and 2 of these cases were \geq Grade 3). The pattern of CRS generally begins 2–12 hours following the first 3 doses of IMCgp100 and the observed toxicities include hypotension (which has been severe in some patients), rash or general erythema, pruritus, facial and general edema, pyrexia and chills. Other commonly reported symptoms, typically mild to moderate, include headache, fatigue, nausea, and vomiting. Grading of CRS is based on the modified grading system ([Table 6-5](#)). Aggressive management in cases of suspected CRS is warranted per guidance in [Table 6-5](#). Early intervention with immunosuppression therapy (e.g., high-dose corticosteroid therapy) is warranted in cases of suspected CRS.

Table 6-4 describes updated grading for events of CRS.

Table 6-4 Cytokine Release Syndrome Grading Scalea

Grade	Symptoms
1	Symptoms are not life-threatening and require symptomatic treatment only (e.g., fever, nausea, fatigue, headache, myalgia, and malaise)
2	Symptoms require and respond to moderate intervention: 
 • Oxygen requirement < 40% • Hypotension responsive to fluids or 1 low-dose vasopressor • Grade 2 organ toxicity
3	Symptoms require and respond to aggressive intervention 
 • Oxygen requirement > 40% • Hypotension requiring high-dose or multiple vasopressors • Grade 3 organ toxicity • Grade 4 transaminitis
4	Life-threatening symptoms 
 • Requirement for ventilator support • Grade 4 organ toxicity (excluding transaminitis)
5	Death

a. Lee 2014.

Table 6-5 Recommended Management and Dose Modifications of IMCgp100 by Toxicity Grade for Study Medications

Worst Toxicity NCI CTCAE v4.03 Grade	Recommended Management and Dose Modifications
Skin Toxicity	
Pruritus	
Grade 1	Continue dosing. If symptomatic, consider systemic antihistamine regimen (see grade 2 guidance below).

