Grade 3	
Hold all doses of IMCgp100 until returned to NCI CTCAE grade ≤ 1.
 
Management:
 
Treat according to institutional practice which generally includes an anti-pruritic regimen (see grade 2 management above). In addition, corticosteroid treatment (oral or topical) can be considered for symptomatic rash that does not respond to anti-pruritic regimen. For topical regimens, refer to grade 2 management above.
 
Oral or topical corticosteroids can be used for bullous formations or blistering. If bullous formation or blistering recur, consult Sponsor Medical Monitor for guidance.

	
Dose adjustments:
 
If grade 3 rash observed with IMCgp100 resolves to NCI CTCAE grade ≤ 1 within 7 days, restart at the same dose level. If grade 3 rash resolves to NCI CTCAE grade ≤ 1 in 7–21 days, restart with 1 dose-level reduction in IMCgp100¹.

Grade 4	
Any grade 4 rash regardless of presentation, permanently discontinue IMCgp100. Manage according to institutional practice, consultation with a dermatologist is recommended.

Hypotension	
Mild, asymptomatic decrease ² : e.g., < 15 mmHg systolic blood pressure Grade 1	
Increase frequency of vital sign assessments to every 2 hours.
 
Consider maintenance intravenous fluids if mild decrease in blood pressure (e.g., systolic blood pressure < 110 mmHg or decrease in SBP of approximately less than 15 mmHg).
 
 Admit for inpatient monitoring (unless already hospitalized per protocol). Consider associated symptoms present and consider diagnosis of cytokine release syndrome (see below) Administer bolus intravenous fluids at a rate of approximately 1 L crystalloid per hour. If hypotension does not resolve with intravenous fluid therapy, consider intravenous corticosteroid therapy (e.g., methylprednisolone 2 mg/kg initial dose or equivalent) 
Consider prophylactic electrolyte supplementation for patients receiving intravenous fluids with low-normal serum phosphorus or magnesium electrolyte levels.

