9.6.2.2 Adverse Events

Summary tables for AEs include only AEs that are new or worsened during the on-treatment period (treatment-emergent AEs). However, all safety data (including those from the pre- and post-treatment periods) will be listed and those collected during the pre-treatment and post-treatment period are to be flagged.

The incidence of treatment-emergent AEs will be summarized by system organ class and/or preferred term, severity (based on NCI CTCAE v.4.03 grades), type of AE, and relation to study treatment by treatment group. Deaths reportable as SAEs and non-fatal SAEs will be listed by patient and tabulated by type of AE and treatment group.

Definitions of notably abnormal vital signs results (e.g., hypotension) will be specified in the SAP and a shift table baseline to worst on-treatment result will be produced by the Phase 1 dose escalation and Phase 2 dose expansion groups.

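### Section 6.2 counts any medically treated hypotension at C1D15 as CTCAE grade 2 or more, while Table 6-5 labels a mild fall treated with bolus fluids Grade 1, so the C1D22 inpatient trigger is ambiguous

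*Protocol*

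**What the plan says.** **Section 6.2, C1D22 rules.** Item 1 allows outpatient C1D22 when the C1D15 dose raises no safety concern and the patient "does not experience an adverse reaction involving hypotension of grade 2 or greater". Item 2 makes inpatient monitoring at C1D22 mandatory: "If the patient experiences hypotension requiring any medical intervention (Common Terminology Criteria for Adverse Event [CTCAE] grade 2 or greater) at C1D15". Item 2 then releases the patient to outpatient dosing if no hypotension needing intervention occurs at C1D22. That release condition carries no grade.

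**Table 6-5 (printed under Section 6.9.2).** The grade column is headed "Worst Toxicity NCI CTCAE v4.03 Grade". The first hypotension row is a mild, asymptomatic decrease, for example "< 15 mmHg systolic blood pressure Grade 1". For that row the table lists more frequent vital signs, consideration of maintenance fluids, and admission if the patient is not already in hospital. It then says "Administer bolus intravenous fluids at a rate of approximately 1 L crystalloid per hour" and adds "If hypotension does not resolve with intravenous fluid therapy, consider intravenous corticosteroid therapy". The next row labels an asymptomatic fall of 15 to under 35 mmHg Grade 2 and has its own fluid and steroid text. Footnote 2 describes the mmHg changes as management guidance to be read in clinical context.

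**Section 6.9.1.** Aggressive intravenous fluid is the initial therapy for low-grade hypotension.

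**Table 7-1 footnote d and Table 7-3.** Both require inpatient C1D22 after grade 2 or greater hypotension at C1D15. Neither mentions intervention.

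**Sections 6.4 and 9.6.2.2.** Section 6.4, on dose-limiting toxicities, sets CTCAE v4.03 for all grading unless otherwise specified. Section 9.6.2.2 summarizes adverse events by "severity (based on NCI CTCAE v.4.03 grades").

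**The concern.** Section 6.2 item 2 and Table 6-5 name the same scale but sort hypotension on different bases. Item 2 sorts by whether the event needed treatment. Table 6-5 sorts by the size of the fall and by symptoms, and puts active treatment in its lowest row. An event in that row, treated as the row describes, satisfies item 2's intervention wording while carrying a Grade 1 label.

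The grade decides where the next dose is given. Section 6.2 links the inpatient rules to hypotension, and Section 6.9.1 reports severe cases across the programme. Two sites with identical patients could schedule C1D22 differently, each citing the protocol.

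**Working it through.** The plan states no figure on this point and no arithmetic applies. The check takes one event through each rule.

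**Event.** At C1D15 a patient has an asymptomatic systolic fall of less than 15 mmHg and receives bolus intravenous fluid. All patients are already inpatients at C1D15, so the admission step in the Table 6-5 row adds nothing here. The relevant interventions are the fluids and, if they fail, possible steroids.

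| Place | Basis of the rule | Result for this event |
|---|---|---|
| Table 6-5, first hypotension row | Size of fall, no symptoms | Grade 1 |
| Section 6.2 item 2 | Any medical intervention required, equated with grade 2 or more | Grade 2 or more; C1D22 must be inpatient |
| Section 6.2 item 1 | No grade 2 or more, and no safety concern | With the Table 6-5 grade, outpatient C1D22 is allowed if no safety concern is raised |
| Table 7-1 footnote d | Grade 2 or more | With the Table 6-5 grade, inpatient C1D22 is not required |
| Table 7-3, C1D22 row | Grade 2 or more | As footnote d |
| Table 7-3, Cycle 2 and later row | One-hour outpatient rule, for patients with neither grade 2 or more at C1D15 nor grade 3 or 4 at the first three doses | Covered with the Table 6-5 grade; not covered if graded 2 |

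**Reverse case.** Table 6-5 footnote 2 says patients with baseline hypertension may need no intervention for mild or moderate falls. An untreated asymptomatic fall of 15 to under 35 mmHg is then Grade 2 by the table, but does not meet item 2's intervention wording. The two bases can therefore disagree in either direction.

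**Extraction check.** The tables were read from PDF, so the bullet layout of the first hypotension row may be imperfect. The fluid and steroid text nevertheless comes before a separate Grade 2 row with its own fluid and steroid text. Section 6.9.1 independently gives fluids for low-grade hypotension, although it attaches no number to that term.

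**Rules not touched.** The 8-hour observation through C2D15 and the inpatient rule after a treatment break depend on grade 3 or 4 hypotension. A Grade 1 versus Grade 2 disagreement does not change them.

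**The case against.** The strongest reply is that Table 6-5 is a management table. Its title concerns recommended management and dose modifications, its hypotension figures are given as examples, and footnote 2 calls them guidance. For cytokine release syndrome the protocol expressly supplies a substitute scale in Table 6-4; it declares none for hypotension. On this reading CTCAE v4.03 governs, and every C1D22 rule shares one threshold, grade 2 or greater. Item 1 also withholds outpatient dosing when C1D15 raised a safety concern, and a patient who needed bolus fluids may well fail that condition.

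Much of this stands. The nominal threshold is the same throughout, outpatient C1D22 is not automatic for the traced patient, and the first hypotension row may describe escalating steps rather than treatment for every mild fall. But the rows still carry numbered grades in a column headed CTCAE v4.03, so a site using them could reasonably believe it is applying CTCAE. Item 2 is mandatory and turns on intervention, while Table 7-1 footnote d and Table 7-3 carry no safety-concern condition. The reply narrows the conflict without removing it.

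A reader might also infer that the reported severity distribution of hypotension will be biased. The protocol does not support that: Section 9.6.2.2 already fixes CTCAE v4.03 for the summaries, and no text tells sites to take adverse event severity from the mmHg rows.

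**Conclusion.** The inconsistency is real and worth correcting, but it is narrow. It concerns how a mild, fluid-treated fall at C1D15 is graded for the C1D22 monitoring trigger, and for the one Cycle 2 and later row of Table 7-3 that refers to grade 2. It rests on reading bolus intravenous fluid as a medical intervention and on the row order of Table 6-5 as extracted.

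Its size in patients is unknown. A reader might apply an assumed event rate to the approximately 150 expansion patients, but the protocol gives no frequency for falls under 15 mmHg at C1D15 or for fluid use in them, so any such count would be a guess. Nor does the conflict extend to hypotension monitoring in general, since the rules keyed only to grade 3 or 4 are unaffected. The ORR analysis and the sample size are not involved.

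The protocol does not reproduce the CTCAE definitions for hypotension, so no view is taken on which of the two places grades the event correctly.

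**What to change.** Reconcile Section 6.2 items 1 and 2, Section 6.9.1, the hypotension rows of Table 6-5, Table 7-1 footnote d and Table 7-3 (the C1D22 row and the Cycle 2 and later row) on one stated grading basis for the monitoring trigger. If the mmHg rows of Table 6-5 are meant as management tiers, remove or relabel their CTCAE grade labels so that sites do not grade from them. Sections 6.4 and 9.6.2.2 need no change, because they already name CTCAE v4.03.

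Which threshold triggers inpatient monitoring is for the clinical team to decide.

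The cost is wording in two sections and three tables, plus a matching grading instruction in the eCRF guidance. No analysis, endpoint or sample size changes.

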6 STUDY TREATMENTS AND ADMINISTRATION

6.1 Study Treatment

For this study, the investigational drug refers to IMCgp100. Study drug will be supplied by the Sponsor, Immunocore.

All dosages prescribed and dispensed to patients and all dose changes during the study must be recorded on the Dosage Administration Record electronic case report form (eCRF).

Table 6-1 Dose and Treatment Schedule

Phase	Study Treatments	Pharmaceutical Form and Route of Administration	Dose	Frequency and/or Regimen
1	IMCgp100	Concentrate for solution for infusion (single use vials)	20 mcg Cycle 1 Day 1 and 30 mcg Cycle 1 Day 8 then, Dose as determined by cohort from Cycle 1 Day 15 and thereafter (refer to Table 6-2 for Dose Levels)	Every week
2	IMCgp100	Concentrate for solution for infusion (single use vials)	20 mcg Cycle 1 Day 1 and 30 mcg Cycle 1 Day 8 then 68 mcg from Cycle 1 Day 15 and thereafter	Every week

For all study medication administration, a physician must be present at the site or immediately available to respond to emergencies during all administrations of all study medications. Fully functional resuscitation facilities should be available.

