3. Hospitalization at other days (e.g., Cycle 2 and beyond) are determined at the discretion of the principal investigator based on the patient's history and tolerance for the initial doses of the study medication with the exception of patients experiencing a treatment delay (please refer to bullet 5 below)
4. Until Cycle 2 Day 15 (C2D15), patients who have experienced a prior CTCAE grade 3 or 4 hypotension event with IMCgp100 dosing and are receiving a dose in the outpatient setting, must be observed in the clinic for a minimum of 8 hours after completion of the IMCgp100 dose.
5. Patients experiencing a break or delay in treatment for any reason of more than 2 weeks AND have a history of a grade 3 or 4 hypotension event with IMCgp100 dosing during the first weeks of treatment will be monitored as an inpatient for the dose subsequent to the break in dosing, regardless of the timing of the break in dosing.

Due to the risk of hypotension, all patients receiving anti-hypertensive medications must **discontinue all anti-hypertensive therapy** for 24 hours prior to dosing and for 24 hours after dosing for the first 6 QW doses of IMCgp100 unless discussed and agreed with the Sponsor's Medical Monitor. After the sixth weekly dose, anti-hypertensive therapy can be restarted on a continuous basis thereafter with the dosing of IMCgp100 (eliminating the 24 hour hold during IMCgp100 dosing) at the discretion of the principal investigator.

In addition, due to the risk of hypotension, IV fluids may be administered prior to IMCgp100 administration and, if given, IV fluids will be recorded as a concomitant medication in the eCRF. The administration of IV fluids should be guided by clinical evaluation and the volume status of the patient. Pruritus is a common adverse event with IMCgp100, so premedication with an antihistamine may be considered. See [Table 6-3](#) for further recommendations regarding treatment of skin toxicity. If a patient experiences an infusion reaction, he/she may receive premedication on subsequent dosing days after consultation with the Sponsor Medical Monitor. Pre-medications should include, but are not limited to, paracetamol/acetaminophen and an antihistamine. Corticosteroid premedication should be avoided; corticosteroids should only be considered if the paracetamol/acetaminophen and antihistamine combination is not effective and only after consultation with the Sponsor Medical Monitor.

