If 2 or more patients experience moderate-to-severe acute infusion reactions on C1D1 or if > 25% of patients experience mild infusion reactions, then mandatory primary prophylaxis regimens (i.e., before dosing on C1D1 or C1D15) will be instituted for subsequent patients beginning treatment after discussion and agreement among principal investigators and the Sponsor. Primary and secondary prophylaxis regimens will include both paracetamol/acetaminophen and an antihistamine. The decision taken to mandate primary prophylaxis will be communicated in writing to all principal investigators participating in the study.

Acute allergic reactions should be treated as needed using institutional guidelines. In the event of anaphylactic/anaphylactoid reactions, any therapy necessary to restore normal cardiopulmonary status should be implemented immediately. Such acute allergic reactions will be reported to the Sponsor in an expedited manner. These should be designated as reportable as a SAE regardless of hospitalization as medically important events. Please refer to SAE reporting section for details. The individual symptoms of

the infusion-related reaction should be captured in order to best characterize the study drug infusion reactions, unless the investigator considers another category, such as “allergic reaction,” “anaphylaxis,” or “cytokine release syndrome” more appropriate in a specific situation.

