Tumor flare	Grade 3 inflammatory reaction at a tumor site associated with a local anti-tumor immune response is a DLT if not resolved to grade ≤ 2 within 7 days
Electrolytes	NCI CTCAE grade 3 electrolyte abnormalities are DLTs if they persist > 7 days despite treatment or are clinically significant. Grade 4 electrolyte abnormality of any duration is a DLT
Rash and/or photosensitivity	NCI CTCAE grade 3 rash is a DLT if rash persists > 7 days despite optimal treatment. Grade 4 cutaneous toxicity of any duration is a DLT
Fatigue	Fatigue is a DLT if it is NCI CTCAE grade ≥ 3 and lasts > 7 days
Infusion-related reaction	Grade 3 infusion-related reaction will not be considered a DLT if resolved with appropriate medical management within 6 hours of occurrence. Grade 4 infusion reaction is a DLT
Other AEs	Other clinically significant toxicities, including a single event or multiple occurrences of the same event that lead to a dosing delay of > 7 days in Cycle 1, may be considered to be DLTs by the investigators and Sponsor, even if not

	NCI CTCAE grade 3 or higher. Infusion reactions will not be considered as dose limiting because they are idiosyncratic and not related to dose
--	------------------------------------------------------------------------------------------------------------------------------------------------

AE = adverse event; ALT = alanine aminotransferase; DLT = dose limiting toxicity; NCI CTCAE = National Cancer Institute Common Terminology Criteria for Adverse Events.

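### Mandatory primary prophylaxis in Section 6.2 leaves out C1D8, both in the doses it covers and in its moderate-to-severe trigger, although the protocol places early toxicity at C1D1 and C1D8

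*Protocol*

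**What the plan says.** The rule is one sentence in Protocol Section 6.2. Its trigger has two arms: "If 2 or more patients experience moderate-to-severe acute infusion reactions on C1D1 or if > 25% of patients experience mild infusion reactions". If either is met, "then mandatory primary prophylaxis regimens (i.e., before dosing on C1D1 or C1D15) will be instituted for subsequent patients", once the principal investigators and the Sponsor have discussed and agreed it. The regimen is paracetamol/acetaminophen plus an antihistamine, and all principal investigators are told in writing.

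Earlier in the same section, patients are to receive "IMCgp100 on C1D1 and C1D8 at 20 mcg and 30 mcg per week, respectively". The next sentence states: "The majority of moderate-to-severe toxicity associated with IMCgp100 in the FIH study was observed at these 2 dose time points". Overnight hospitalization with vital signs at least every 4 hours is then required "after the first administration of IMCgp100 (C1D1), after the second administration (C1D8), and after the escalated dose of IMCgp100 on C1D15 is administered".

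For individual patients the section is permissive: "If a patient experiences an infusion reaction, he/she may receive premedication on subsequent dosing days after consultation with the Sponsor Medical Monitor". An antihistamine may also be considered because pruritus is common.

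**The concern.** The first arm of the trigger looks for moderate-to-severe reactions on one dosing day, and the prophylaxis reaches two. The dose missing from both is one of the two that the section itself names for most moderate-to-severe toxicity. A moderate-to-severe reaction that first appears at C1D8 does not count toward the two-patient threshold. A patient who starts after the rule is in force would have mandatory premedication at C1D1 and C1D15 but not at C1D8. What is at stake is patient safety at a single dose. The response endpoint, sample size and analyses are not involved.

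**Working it through.** No arithmetic applies. The protocol states no infusion-reaction rate by dosing day in its visible text, and the rule rests on no computed figure. The check is to set the rule beside what the protocol says about early toxicity and monitoring.

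**The rule (Section 6.2)**
- Moderate-to-severe trigger: C1D1 only.
- Mild trigger (more than 25% of patients): no day stated.
- Coverage: C1D1 or C1D15. The phrase is introduced by i.e., so it defines the doses and does not merely give examples.

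**Where the protocol places early toxicity**
- Section 6.2: the majority of moderate-to-severe toxicity in the first-in-human study was at C1D1 and C1D8. The listed events are hypotension, rash, pruritus, fever and chills.
- Synopsis, study rationale: the more severe, dose-limiting toxicity was confined to the first two weeks, at C1D1 and C1D8.
- Amendment 1 rationale: uveal melanoma patients in the first-in-human study had infusion-related toxicity at C1D1 or C1D8, including fever, facial edema and hypotension.
- Section 6.9.2: cytokine release syndrome generally follows the first three doses.

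**How C1D8 is treated elsewhere**
- Section 6.2 and Table 7-3: the same inpatient stay, 4-hourly vital signs and at least 16 hours of monitoring as at C1D1 and C1D15.
- Table 6-1: "20 mcg Cycle 1 Day 1 and 30 mcg Cycle 1 Day 8 then 68 mcg from Cycle 1 Day 15 and thereafter". C1D8 is thus itself a step up, from 20 to 30 mcg.

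**Result.** Of the two doses named for most moderate-to-severe toxicity, the moderate-to-severe trigger counts one and the prophylaxis covers one. Of the three mandatory inpatient doses, the prophylaxis covers two, and C1D8 is the exception.

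**Can the omission be read as deliberate?** One reading is that the rule protects first exposure and first escalation. It does not fit well. C1D8 is also an increase, and Table 6-3 says of infusion reactions: "Infusion reactions will not be considered as dose limiting because they are idiosyncratic and not related to dose". If dose matters, C1D8 has a claim to be covered. If it does not, the size of the step at C1D15 is no reason to cover that dose and skip C1D8. The visible text gives no other reason.

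**The case against.** The strongest objection is that two kinds of event are being merged. The first-in-human statement in Section 6.2 concerns toxicity in general, while the trigger concerns acute infusion reactions. Table 6-5 treats reactions during infusion separately from hypotension and from cytokine release syndrome, and no visible text tabulates acute infusion reactions by dosing day. This stands in part, because the evidence for C1D8 is less direct than a day-by-day table would be. It does not remove the mismatch. The Amendment 1 rationale speaks specifically of infusion-related toxicity at C1D1 or C1D8, and the Amendment 4 change list describes infusion-related reactions as generally seen 2–24 hours after the dose, not only during the infusion.

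The second objection is that C1D8 is already protected. The dose was lowered to 30 mcg, the patient is an inpatient, antihypertensives are held unless agreed otherwise with the Medical Monitor, and a patient who reacted at C1D1 may be premedicated. The more-than-25% arm can count mild reactions on any day, and the agreement step lets the investigators and Sponsor add C1D8. All of this stands and makes the gap small. None of it is mandatory primary prophylaxis, because the individual premedication is optional and, for infusion reactions, follows a reaction in that same patient.

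A reader might infer that patients at C1D8 are left unprotected, or that a definite number of reactions would be prevented. The documents support neither. The safeguards above are real, much of the Section 1.4 safety data is redacted, and nothing visible shows how far paracetamol plus an antihistamine would reduce reactions at C1D8. Hypotension, the main early concern, is managed with fluids, corticosteroids and vasopressors. Nor does the protocol contradict itself outright: nothing in it says prophylaxis must cover every dose with early toxicity.

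**Conclusion.** The point holds as a minor design weakness. Read literally, the rule in Section 6.2 omits C1D8 from its moderate-to-severe trigger and from its coverage, while the protocol places early infusion-related and moderate-to-severe toxicity at C1D1 and C1D8 and monitors C1D8 like C1D1 and C1D15. The practical gap is a patient without a reaction at C1D1, not premedicated by choice, who first reacts at C1D8 while already an inpatient. The safety benefit of closing it is small and cannot be quantified from the visible text. The conclusion assumes that the first-in-human timing of toxicity is a fair guide to when infusion reactions occur under the 20 mcg and 30 mcg doses, and that the parenthesis is applied as written. No efficacy analysis is affected.

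**What to change.** Make two changes in the prophylaxis sentence of Section 6.2:

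1. Change the covered doses to C1D1, C1D8 and C1D15.
2. Change the moderate-to-severe trigger from reactions on C1D1 to reactions on C1D1 or C1D8, so that the signal is counted where it is expected.

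Leave unchanged the regimen, the threshold of 2 patients, the more-than-25% arm and the agreement between investigators and Sponsor.

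The cost is one extra paracetamol/antihistamine premedication for each patient who starts after the rule is activated, and none if it never is. The two-patient threshold may be reached somewhat sooner because two dosing days are counted. The objective response rate, the sample size and every planned analysis stay as they are.
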